12.2.1.1.2 Primary Efficacy Hypothesis

The primary hypothesis is that TAVI with the TriGUARD 3 system is superior to standard (unprotected) TAVI for the primary hierarchical composite efficacy endpoint of all-cause mortality or any stroke at 30 days (Tier 1), NIHSS worsening from baseline assessed at 2-5 days post-procedure (Tier 2), freedom from any cerebral ischemic lesions detected by diffusion-weighted magnetic resonance imaging (DW-MRI) 2 to 5 days post-procedure (Tier 3), and total volume of post-procedure cerebral ischemic lesions detected by DW-MRI (Tier 4).

Specifically, the primary efficacy hypotheses are:

H_0 : The hierarchical composite of death/stroke, NIHSS worsening, freedom from any lesions detected by DW-MRI, and larger total lesion volumes is not different between Intervention and Control groups

H_1 : The hierarchical composite of death/stroke, NIHSS worsening, freedom from any lesions detected by DW-MRI, and larger total lesion volumes is lower in the Intervention group than in the Control group

The null hypothesis will be tested at the final analysis at a one-sided 0.025 level of significance. The null hypothesis will be tested using the chi-square test according to the method described in Finkelstein-Schoenfeld² and Pocock⁷⁷.

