Simple mean		1.32%	3.6%	3.6%	5.66%
Weighted mean		1.33%	3.21%	5.09%	7.25%
Meta-analytic mean*		1.6%	3.83%	5.09%	7.26%

* Embol-X excluded

A recently published letter¹⁰⁴ presented a meta-analysis of the above trials for the primary end point of death and stroke at longest follow-up available, showed rates of 6% vs 10% for device vs. control respectively.

Based on the above, and considering SENTINEL being the most recent trial (with up to 9% stroke rate and 1.8% death rate in the controls), we conservatively estimate an ~11% rate of all-cause mortality or stroke at 30 days in subjects undergoing unprotected TAVI and a 50% reduction yielding a ~6% assumed event rate in the protected group.

The remaining component event rates (Tiers 2-4) are estimated based on data from the above mentioned trials, which employed identical NIHSS assessments and DW-MRI analysis methodology.

We conservatively expect 9% of controls and 6% of device group patients to have any NIHSS worsening ([table 6b](#)).

Among subjects who survived free of stroke to 30 days, and who did not experience NIHSS worsening at the post-procedure (2-5 days post-procedure) assessment (Tier 3 of the hierarchy), we expect 11% of controls and 27% of device group patients to be free of any lesions on MRI. These assumptions are based on the above trials and more specifically on the published results of DEFLECT III⁸ (Per Treatment) which used a similar device with full cerebral protection (as opposed to SENTINEL) and the same MRI assessment modality as planned in this trial (see also [table 6a](#)).

Among patients surviving without stroke at 30 days, and who did not experience NIHSS worsening, and who had MRI lesions on DW-MRI (final 4th Tier) we expect the rates of lesion volumes categorized by size in pre-specified set ranges of >0-50 mm³, >50-150 mm³ and above 150 mm³ to be 7%, 33%, and 48% in the controls, respectively, and 19%, 7.5% and 46% in the device arm, respectively. Expected rates were adapted from DEFLECT III (Per Treatment), the only published study thus far to incorporate such volume subdivisions.⁸

All tiers and their respective assumed rates are presented in [table 11b](#).

Table 11b. Assumed event rates

	Assumed Control Rates	Assumed TriGUARD 3 Rates
Death or Stroke	11%	6%
Worsening NIHSS	9%	6%
Freedom from MRI Findings (Lesion Volume 0 mm³)	11%	27%
Lesion Volume (mm³)		
>0-50	7%	19%
>50-150	33%	7.5%
> 150	48%	46%

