- If both had a stroke on same day, the comparison moves on to the next tier.
- Assuming neither experiences a stroke or death before 30 days, if Subject A experiences NIHSS worsening, and Subject B does not experience NIHSS worsening, Subject A loses (score -1) and Subject B wins (score +1). In case both have NIHSS worsening the patient with the lesser worsening wins.
- Assuming neither subject experiences a stroke or death before 30 days or NIHSS worsening from baseline, if Subject A has no cerebral ischemic lesions on DW-MRI and Subject B has a cerebral ischemic lesion on DW-MRI, Subject A wins (score +1) and Subject B loses (Score -1).
- Assuming neither subject experiences a stroke or death before 30 days, NIHSS worsening from baseline or freedom from DW-MRI cerebral ischemic lesions, if Subject A has a total cerebral ischemic lesion volume of 50 mm³ and Subject B has a total cerebral ischemic lesion volume of 100 mm³, Subject A wins (score +1) and Subject B loses (Score -1).

An illustration of this algorithm is provided in Figure 4 below.

Figure 4. Algorithm of assigning scores by the Finkelstein and Schoenfeld method (*Note: each patient from the intervention group is compared with each and every patient from the control group*)

After all between-subject comparisons have been performed, scores are summed to obtain a cumulative score for each subject, and outcomes between treatment groups are then compared by chi-square test.

This analytic approach does not result in a natural point-estimate (e.g., proportion, mean, median, time-to-event); however, Pocock et al. provided a computational framework for the test statistic called "win ratio". In brief, it is calculated as a proportion of "wins" for each group out of the total number of the pairwise comparisons.

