In the final analysis, assessment of treatment-by-study-center and treatment-by-region on the primary efficacy endpoint will be carried out on the eITT population using quantile regression. Total score obtained for each subject using the proposed approach (Finkelstein and Schoenfeld) will be the model dependent variable. The following two models will be built: 1.) Model inclusive of treatment, study center, and treatment-by-study center interaction, and 2.) Treatment region (US versus OUS, Phase I only), and treatment-by-region interaction. A 0.15 level of significance will be used to assess the significance of each of the study center and region effects on the efficacy endpoint. A non-significant result for each of study center and region will support the pooling of patients across study centers and across regions for the primary efficacy analysis. A significant result will require further inspection of the by-center and by-region results to assess if poolability is appropriate. Note that centers with less than 5 subjects will be pooled with other centers by closest geographic region; this pooling will be carried out prior to the unblinding.

Additionally, an assessment of treatment-by-study-center and treatment-by-region on each component of the primary efficacy endpoint will be carried out on the eITT population using analysis of variance on the cube root transformation for total lesion volume data and logistic regression for death/stroke and NIHSS worsening, with effects for 1.) Treatment, study center, and treatment-by-study center interaction, and 2.) Treatment, region (US versus OUS, Phase I only), and treatment-by-region interaction. As above, a 0.15 level of significance will be used to assess the significance of the interaction; a non-significant interaction or an interaction that is significant but only quantitative (and not qualitative) in nature will support the pooling of patients across study centers and across regions for the primary analysis; and centers with less than 5 subjects will be pooled with other centers by closest geographic region, with pooling carried out prior to the unblinding.

In addition, the above analysis will be repeated in the eITT population (separately in Phase I and Phase II analysis sets) to assess the consistency of treatment effects on each component of the primary efficacy endpoint across the following variables:

- Subject gender (male versus female)
- Valve prosthesis type (Edwards vs. Medtronic)

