- Operative risk (by Society of Thoracic Surgeons [STS] Risk Score)
- Type and duration of antiplatelet therapy:
 - Pre- and peri-procedural therapy:
 - Protocol-recommended antiplatelet therapy vs. other
 - Maintenance therapy:
 - Dual antiplatelet therapy (DAPT) to 90 days vs.
 - Monotherapy (aspirin or clopidogrel) to 90 days vs.
 - Warfarin with antiplatelet therapy to 90 days vs.
 - Other

As above, analysis of variance on the cube root transformation for total lesion volume data and logistic regression for death/stroke and NIHSS worsening will be used, and a 0.15 level of significance will be used to assess the significance of the interaction.

If the primary efficacy endpoint is met in the primary (eITT) analysis population, sequential testing of the primary efficacy hypothesis will be conducted in the ITT analysis population of evaluable subjects (Roll-In patients are excluded.) As a secondary analysis, the primary efficacy endpoint and its components will be evaluated in the ITT analysis population of evaluable subjects (Roll-In patients are excluded). As an additional analysis, the primary efficacy endpoint will be evaluated in the PT population of subjects with available data.

An additional analysis of the primary efficacy endpoint will also be performed in the primary eITT analysis population with adjustment for pre-existing cerebral lesion volumes. The adjustment will be performed using a quantile regression with the resultant score being the dependent variable and group and the pre-existing cerebral lesion volumes will be independent. Specifically, the PROC QUANTREG procedure will be used to model the median of the score with QUANTILE=0.5 option.

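### The covariate-adjusted analysis of the primary efficacy endpoint models the median Finkelstein-Schoenfeld score, while the primary test compares summed scores; a null adjusted result would say little about robustness

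*Combined protocol and SAP*

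**What the plan says.** Section 12.2.1.1.2 states a null that the hierarchical composite, ending with "larger total lesion volumes is not different between Intervention and Control groups", and continues: "The null hypothesis will be tested using the chi-square test according to the method described in Finkelstein-Schoenfeld". On the level it says: "The null hypothesis will be tested at the final analysis at a one-sided 0.025 level of significance". Section 12.4.3 sums each subject's pairwise scores and then compares the arms. The note to Figure 4 in that section describes the pairs: "each patient from the intervention group is compared with each and every patient from the control group". Section 5.4.1.1.2, however, also speaks of pairwise comparisons among all subjects.

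Section 12.4.3 then adds one analysis in the eITT population that adjusts for pre-existing cerebral lesion volume, with the score as outcome and group and lesion volume as predictors: "Specifically, the PROC QUANTREG procedure will be used to model the median of the score with QUANTILE=0.5 option". No alpha, success rule or power is attached to it.

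The same section uses quantile regression for the treatment-by-center and treatment-by-region models: "Total score obtained for each subject using the proposed approach (Finkelstein and Schoenfeld) will be the model dependent variable". It does not name the quantile there.

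**The concern.** A sum of scores is, apart from scaling, a mean, so every tier contributes to the primary statistic. A median depends only on where the middle subject of each arm falls. Adjusting the median therefore changes two things at once: the covariate is added and the quantity estimated is replaced. If the primary test is positive and the adjusted analysis is not, a reader cannot tell which change was responsible. The natural reading, that the benefit was due to imbalance in pre-existing lesions, could be wrong even if the device works exactly as assumed.

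**Working it through.** **Inputs** (12.2.3, 12.2.4.1.2, Table 11b). Death or stroke 11% control, 6% device. NIHSS worsening among the rest 9% and 6%. No lesion on MRI 11% and 27%. The non-zero volume classes (>0-50, >50-150, >150 mm³) are expected "to be 7%, 33%, and 48% in the controls, respectively, and 19%, 7.5% and 46% in the device arm, respectively". There is a further 30% relative reduction in each volume class. A Tier 4 win needs a 15% relative or 50 mm³ absolute difference. MRI loss is 15% and other loss 5%. Sample size is 150 device against 75 or 138 controls, tested at one-sided 0.025.

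**Where the assumed benefit lies** (no simulation; MRI percentages read as conditional on reaching Tier 3; no missing MRI).
- Reaching the MRI tiers: control 0.89 × 0.91 = 0.81; device 0.94 × 0.94 = 0.88.
- Event-free with volume ≤50 mm³: control 0.81 × 18% = 15%; device 0.88 × 46% = 41%. Gap about 26 points.
- Event-free with volume ≤150 mm³: control 0.81 × 51% = 41%; device 0.88 × 53.5% = 47%. Gap about 6 points.

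Both ≤150 mm³ shares are under 50%, so the middle subject of each arm is in the >150 mm³ class. The largest assumed gain is below that point. What separates the medians is the 6-point shift plus the 30% reduction within the top class.

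**The plan's power figure.** The stated power is >80% with 75 controls and at least 92% with 138. Monte Carlo with an FS z-statistic and permutation variance gave 83-91% and 92-98% when the 30% reduction was included. Without it the stated power was not reached.

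**Median regression of the all-pairs score.** The first set of runs used 600 trials per cell, or 300 for fits with a covariate. It varied the within-class volume distribution, the reading of the win threshold, missing MRI as tie or exclusion, and the test used for the median. The second set also applied the win threshold.

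| Setting | FS test | Median regression |
|---|---|---|
| Full effect, 75 controls, first set | 83-91% | 30-60% |
| Full effect, 138 controls, first set | 92-98% | 27-65%, up to 71% in covariate fits |
| No 30% reduction, first set | 53-61% (75), 71-78% (138) | 10-26% |
| Full effect, second set | 83-99% | 41-79% |
| No 30% reduction, second set | 64-79% | 16-20% |

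In the first set the median model was at least 26 points below the FS test in every completed cell, usually 30-60. The covariate fits with pooled controls, exponential volume tail and 30% reduction did not finish. Monte Carlo error is about 2 points (600 trials) to 3 points (300). One covariate-fit cell gave 79% for the FS test, within that error of 80%.

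**Is the loss due to adjusting or to the median?** Linear regression of the same all-pairs score on group and covariate matched the FS test within about 2 to 3 points. In one cell (138 controls, full effect) the FS test had 97%, linear regression 97% and median regression 70.7%. The median causes the loss.

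**Why the mean keeps the primary quantity.** All-pairs scores sum to zero. If T is the device-arm sum, within-arm comparisons cancel and T is wins minus losses between arms. The difference in mean score is T/150 + T/75 = T × 225/(150 × 75), which is 225 times the net win proportion T/(150 × 75).

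**Why all pairs are needed.** If scores use only device-control pairs, subjects in one arm share the same opposing sample, and regression standard errors ignore this. Under equality with few ties, a score against m opponents has variance about m²/3.
- 150:75, between-arm scores: squared standard error 75²/(3 × 150) + 150²/(3 × 75) = 12.5 + 100 = 112.5. All-pairs scores: (225²/3)(1/150 + 1/75) = 337.5. The ratio is 1/3, so z is inflated by √3 and the one-sided error is P(Z > 1.96/1.73) = 13%.
- 150:138: 42.3 + 54.3 = 96.7 against 384.7. The ratio is 0.25, and P(Z > 1.96/1.99) = 16%.

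Simulation with both arms drawn from control agreed: robust linear regression gave 13% and 16% in one check and 10-16% in another, against about 1.6-3.4% on all-pairs scores. Median regression had 4-25% one-sided error on between-arm scores. On all-pairs scores it had 2-3% (rank test) or 3-6% (Wald test).

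**The case against.** The strongest reply is that this is one supportive analysis with no alpha, and section 12.2.1.1.1 ties trial success only to the two primary endpoints in their primary populations. That stands. Several stronger readings also go beyond the documents.

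- A reader might infer that the median model tests a different null from a stated win/loss null. No such null is stated. Section 12.2.1.1.2 says only that the composite does not differ, and if the score distributions are identical both nulls hold. The difference is in the quantity estimated and in power.
- A reader might infer that the adjusted analysis will usually be null. At the upper end of the range it is more often positive than not.
- A reader might take the low figures without the 30% reduction as the plan's own effect. Section 12.2.4.1.2 includes that reduction.
- A reader might infer from 48% against 46% above 150 mm³ that the medians nearly coincide. With the full effect both medians lie in that class, where the 30% reduction acts directly.
- A reader might extend the point to the center and region models. Section 12.4.3 does not name their quantile, no interaction power was computed, and each component is also assessed by analysis of variance or logistic regression.

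The simulated covariate was unrelated to outcome, so the figures do not show what adjustment for a prognostic covariate would gain.

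**Conclusion.** The point holds as a cheap improvement. The adjusted analysis estimates a difference in median score and the primary test compares summed scores. Power is roughly 27-79% against 83-99% under the full assumed effect, and roughly 10-26% against 53-79% without the 30% reduction. The direction was the same in both sets of runs. The exact size rests on assumptions not in the documents: event timing, NIHSS severity, the within-class volume distribution, missing-MRI scoring, the test used in PROC QUANTREG, and a non-prognostic covariate. A non-significant adjusted result should not be read as evidence against robustness to pre-existing lesion volume. The decision on trial success is untouched.

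**What to change.** In 12.4.3, replace the median model with linear regression of the FS score on treatment and pre-existing lesion volume, using robust or permutation standard errors. State that this score is computed over all pairs of subjects, not only device-control pairs. An FS test stratified by lesion-volume category is an alternative.

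For the center and region models, name the quantile or, for consistency, use the same all-pairs mean-score model. That is a suggestion, not the correction of a demonstrated error.

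The cost is a change of wording and procedure, with no new data. The coefficient becomes a mean rather than a median score difference; dividing it by the number of subjects compared gives the net win proportion.

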12.4.4 Hypothesis-driven Secondary Endpoints

For the following secondary endpoints, a test for superiority of each intervention group to the control group will be performed. To address the issue of multiple tests among these secondary endpoints, sequential testing is planned. Secondary endpoints will be formally tested if and only if the primary study hypotheses are confirmed. The secondary endpoints will be tested individually, in the order in which they are listed as follows:

- **All stroke** [evaluated at 7 days in the eITT population]
- **NIHSS worsening**, defined as any NIHSS score increase from baseline [evaluated at 2 to 5 days post-procedure in the efficacy Intention to Treat (eITT) analysis population]. A sensitivity analysis will further compare ≥ 2 points NIHSS worsening [evaluated at 2-5 days post-procedure in the efficacy Intention to Treat (eITT) analysis population]

- **Composite of all-cause mortality and all stroke** [evaluated at 7 days in the eITT population]
- **CNS Infarction** (NeuroARC defined) [evaluated at 30 days in the eITT analysis population]
- **Total volume of cerebral ischemic lesions** detected by DW-MRI, [evaluated 2 to 5 days post-procedure in the efficacy Intention to Treat (eITT) analysis population]

The above endpoints will be tested by this pre-specified sequence, until the first non-significant difference is found between the two treatment groups. After that, other treatment comparisons will be examined in an exploratory manner.

12.4.5 Exploratory Secondary Endpoints

12.4.5.1.1 Secondary Safety Endpoints

All secondary safety endpoints, including the components of the primary safety endpoint will be reported by treatment group in the AT population of evaluable subjects using appropriate descriptive statistics (sample size, mean, standard deviation, median, minimum, maximum for continuous characteristics; counts and percentages of patients for dichotomous characteristics). No formal hypothesis testing will be performed, and there is no plan to adjust alpha to account for multiple testing of exploratory secondary endpoints.

The AT analysis will be considered primary. As a secondary analysis, all secondary safety and performance endpoints will be evaluated in the ITT population of evaluable subjects.

For safety endpoints occurring in the Intervention and Roll-In groups, relationship to the investigational device/investigational procedure (as determined by an independent Clinical Events Committee [§11.1]) will also be reported.

12.4.5.1.2 Secondary Efficacy Endpoints

- **Imaging Efficacy Endpoints**

All secondary imaging efficacy endpoints will be reported by treatment group in the eITT Population of subjects with available data using descriptive statistics. No formal hypothesis testing will be performed, and there is no plan to adjust alpha to account for multiple testing of exploratory secondary endpoints. Statistics for continuous variables will include mean, median, standard deviation, minimum, maximum, and sample size for each treatment group. Binary variables will be summarized using frequencies, percentages, and sample size for each treatment group.

The eITT analysis will be considered primary. As a secondary analysis, all secondary imaging efficacy endpoints will be evaluated in the ITT population of evaluable subjects. An additional analysis will also be performed in the PT population.

An additional analysis of secondary imaging efficacy endpoints with adjustment for pre-existing cerebral lesion volume will also be performed in the primary eITT analysis population. These endpoints include presence of cerebral ischemic lesions (§□), number of cerebral ischemic lesions (§□), per-patient average single cerebral ischemic lesion volume (§□), single cerebral ischemic lesion volume (§□), and total volume of cerebral ischemic lesions (§□), which vary by their distribution from binary (as in "presence of cerebral ischemic lesions") to Poisson, or possibly negative binomial in others. The choice of a specific model used for adjustment will therefore depend on the actual distribution of the dependent variable (logistic, log-linear, Poisson, negative binomial or quantile). The models will include the study group and pre-existing cerebral lesion volume as independent variables.

- **Neurologic Efficacy Endpoints**

All secondary neurologic efficacy endpoints will be reported by treatment group in the eITT Population of evaluable subjects (Roll-In subjects are excluded) using descriptive statistics. No formal hypothesis testing will be performed, and there is no plan to adjust alpha to account for multiple testing of exploratory secondary endpoints. Statistics for continuous variables will include mean, median, quartiles, standard deviation, minimum, maximum, and sample size for each treatment group. Binary variables will be summarized using frequencies, percentages, and sample size for each treatment group.

The analysis of the eITT population will be considered primary. As a secondary analysis, all secondary neurologic and cognitive efficacy endpoints will be evaluated in the ITT population of evaluable subjects. An additional analysis will also be performed in the PT population.

An additional analysis of secondary neurologic and cognitive efficacy endpoints with adjustment for pre-existing cerebral lesion volume will also be performed in the primary eITT analysis population. As in secondary imaging efficacy endpoints, the distribution of the neurologic endpoints (including NIHSS worsening [§□], and new neurologic impairment [§□]) varies. The models, therefore, will be chosen based on the actual distribution of dependent variable (logistic, log-linear, poisson, negative binomial or quantile), with study group variable and cerebral lesion volume as independent variable.

